PD	Progressive Disease
PET	Positron Emission Tomography
PFS	Progression Free Survival
p.o.	peros/by mouth/orally
PR	Partial Response
RC	Regional Control
RCB	Residual Cancer Burden
RECIST	Response Evaluation Criteria in Solid Tumors
RR	Regional Recurrence
SAE	Serious Adverse Event
SCCC	Simmons Comprehensive Cancer Center
SD	Stable Disease
SEER	Surveillance Epidemiology and End Results
SGOT	Serum Glutamic Oxaloacetic Transaminase
SPGT	Serum Glutamic Pyruvic Transaminase
VHI	Voice Handicap Index
VMAT	Volumetric Modulated Arc Therapy
WBC	White Blood Cells

STUDY SCHEMA

STUDY SUMMARY

Title	Phase II Trial of Stereotactic Body Radiotherapy (SBRT) for Early- stage Glottic Larynx Cancer
Short Title	A Prospective Phase II Trial of SBRT for Early Glottic Larynx Cancer
Protocol Number	122017-043
Phase	Phase 2
Methodology	Prospective Study
Study Duration	3 years to accrue plus additional 3 years of follow-up
Study Center(s)	Single center
Objectives	To determine the local control and quality-of-life outcomes of using SBRT for early-stage glottic larynx cancer
Number of Subjects	25
Diagnosis and Main Inclusion Criteria	Stage I-II glottic larynx cancer
Study Product(s), Dose, Route, Regimen	Highly focal SBRT, delivered either every other day (low-risk) or daily (moderate-risk)
Duration of administration	3 weeks
Reference therapy	N/A
Statistical Methodology	The study has 85.6% power to detect a local control probability difference of 15% (95% vs. 80%) using a two-sided, one-sample log-rank test at a 0.10 significance level.

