5.3 Follow-up Procedures

Patients will be seen by a radiation oncologist at 1 month (+/- 1 week) and 3 months (+/- 1 week) from the completion of treatment. More frequent visits are encouraged if the patient requires additional help with recovery and rehabilitation

Patients will then be seen every 3 months (+/- 2 weeks) for the first year, and then at least every 6 months (+/-2 weeks) until the end of the 3rd year. Subsequent and intervening follow-up visits will be made per physician preference. These protocol mandated procedures will occur at each follow-up:

- Interim history
- Physical exam, vital signs, ECOG PS (vital signs are not required when patient has a Telehealth visit)
- Laryngoscopy to assess tumor response and toxicity
- Quality of life and voice quality assessment (months 1, 3, 6, 12, 18, 24 and 36)

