10.0 STATISTICAL CONSIDERATIONS

10.1 Study Design/Study Endpoints

- 10.1.1 Primary endpoint: 2-year risk of local failure (i.e. anywhere in the larynx) following SBRT treatment of early glottic larynx cancer
- 10.1.2 Secondary endpoints:
 - 10.1.2.1 Patient-reported outcomes: Difference in PRO measures between baseline and 1, 3, 6, 12, 18, 24 and 36 months following treatment:

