10.2 Sample Size and Accrual

The general perception in the radiotherapy community is that radiotherapy for early stage glottic larynx cancer leads to a local control probability of approximately 95%. Given there are some T2 patients on the study (bigger tumors), we use the 2-year local control rate of 90% rather than 95% with the non-inferiority margin of 15%. The hazard rates for 2-year local control probabilities of 90% and 75% are 0.0527 and 0.1438, respectively. With a sample size of 25 patients, this study has more than 80% power to detect a non-inferiority against an upper hazard ratio bound of 2.73 (=0.1438/0.0527) using a log-rank test at a significance level of 0.1 when the actual hazard ratio is 1.0 and the reference group hazard rate is 0.0527. Patients will be accrued for a period of 3 years with 2-year follow-up. This assumes that a local control outcome inferior to 75% would obviate the potential benefit of highly focal radiation treatment.

Our prior phase I study included a nearly identical patient population and took just over 3 years to complete; however, this protocol has 2 periods of a 90 day halt on new accrual because it was a phase I study. Therefore we expect the present proposal to be completed in 2.5 to 3 years.

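### The Study Summary's 85.6% power (95% vs 80% local control) is not the power of the design in Section 10.2 (90% vs 75%, same 25 patients), and Section 10.3.1 names neither test nor threshold

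*Combined protocol and SAP*

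**What the plan says.** The Statistical Methodology row of the Study Summary gives "85.6% power to detect a local control probability difference of 15% (95% vs. 80%) using a two-sided, one-sample log-rank test", at a 0.10 level, with 25 subjects and 3 years of accrual plus 3 of follow-up. It gives no time point for the two rates and does not say which is the null.

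Section 10.2 starts from a perceived 95% control rate and moves away from it because some T2 patients are enrolled: "we use the 2-year local control rate of 90% rather than 95% with the non-inferiority margin of 15" percent. It converts 90% and 75% at 2 years to hazards of 0.0527 and 0.1438 and states that "this study has more than 80% power to detect a non-inferiority against an upper hazard ratio bound of 2.73", "using a log-rank test at a significance level of 0.1 when the actual hazard ratio is 1.0". On timing it says "Patients will be accrued for a period of 3 years with 2-year follow-up". It explains the lower value: "This assumes that a local control outcome inferior to 75% would obviate the potential benefit of highly focal radiation treatment". It does not state the side of the test or call it one-sample.

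The primary endpoint in Section 10.1.1 is the "2-year risk of local failure (i.e. anywhere in the larynx) following SBRT treatment of early glottic larynx cancer". Visits continue "at least every 6 months (+/-2 weeks) until the end of the 3rd year" (Section 5.3; Section 4.6 agrees). Section 10.3.1 says the endpoint will be estimated by cumulative incidence with death as a competing risk. It gives no test, level, null value or success criterion.

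**The concern.** The trial has one cohort, and its primary conclusion rests on comparing one rate with a fixed value. The protocol gives two such values, 80% and 75%, two expected rates, 95% and 90%, and two power figures, all for 25 patients. Section 10.2 gives a reason for its choice; the Summary gives none for 80%.

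Two things are at stake. A reader of the Summary will credit the trial with 85.6% power that does not belong to the justified design. The threshold is also unsettled: true control of 80% is better than the 10.2 bound but equals the Summary's null if 80% is the null. Since Section 10.3.1 carries neither value forward, the choice could be made after the data are seen.

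**Working it through.** **Inputs.** n = 25, level 0.10 and 3-year accrual (Study Summary, 10.2); local control of 95%, 90%, 80% and 75%; further follow-up f of 2 years (10.2) or 3 years (Summary). Assumptions: the Summary's rates are 2-year rates, accrual is uniform, failure times are exponential, and there are no losses or competing deaths.

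**Hazards.** λ = −ln(S)/2 gives 0.02565 (95%), 0.0527 (90%), 0.1116 (80%) and 0.1438 (75%). The ratio 0.1438/0.0527 = 2.73 reproduces 10.2.

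**Expected failures.** With accrual a = 3, the probability of an observed failure is 1 − [e^(−λf) − e^(−λ(a+f))]/(λa). With d the expected failures at the true rate and E the count expected under the null over the same follow-up, formula B is power = Φ((E − d)/√E − z). Here z is 1.2816 (one-sided) or 1.6449 (two-sided). Simulations used Z = (O − E)/√E.

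**The Summary's own figure (null 80%, true 95%).**
- Formula B, 3+2 years: d = 2.14 and E = 2.14 × 0.1116/0.02565 = 9.31, so (9.31 − 2.14)/√9.31 = 2.35. Power is 85.7% one-sided and 76.0% two-sided. Two-sided with 3+3 years it is 84.2%.
- Formula A, Φ(((1 − HR)√E0 − z)/√HR), 3+2 years: E0 = 8.00 failures expected under the null and HR = 0.02565/0.1116 = 0.230, giving 86.7% two-sided.
- Simulation, two-sided, 3+2 years: about 90%.

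So 85.6% lies within the range of reasonable methods. It does not reveal which method or follow-up was used.

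**The 10.2 design (null 75%, true 90%), 3+2 years.** d = 25 × 0.1675 = 4.19 and E = 4.19 × 2.73 = 11.43, so (11.43 − 4.19)/√11.43 = 2.14. Formula B gives Φ(2.14 − 1.28) = 80.6% one-sided and Φ(2.14 − 1.64) = 69.1% two-sided. Simulation gives 89.2% and 77.7%. Formula A, which gave 86.7% on the Summary's rates, gives 71.1% two-sided here.

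**The Summary's test at the 10.2 expectation (null 80%, true 90%), 3+2 years.** E = 4.19 × 0.1116/0.0527 = 8.87, so (8.87 − 4.19)/√8.87 = 1.57 and Φ(1.57 − 1.64) is about 47% two-sided. Simulation gives 48.2%.

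**Dependence on follow-up counted** (power in %; the middle columns show formula B / simulation):

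| Follow-up counted | 90 vs 75, one-sided | 90 vs 75, two-sided | Null 80, true 90, two-sided (simulation) |
|---|---|---|---|
| 3+2 years, all | 80.6 / 89.2 | 69.1 / 77.7 | 48.2 |
| 3+3 years, all | 86.8 / 93.8 | 77.5 / 86.1 | 57.9 |
| 3+2, capped at 36 months | 74.8 / 85.6 | 61.9 / 72.4 | 38.5 |
| 3+3, capped at 36 months | 76.4 / 85.4 | 63.9 / 70.5 | 49.0 |
| Capped at 24 months | 64.6 / 76.4 | 50.4 / 53.8 | 27.3 |

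Formula and simulation differ because few failures are expected (about 4 at 90% control with 3+2 years). As a cross-check on the 24-month row, an exact binomial rule of 3 or fewer failures in 25 has size 0.096 at 25% failure and power 0.764 at 10% failure.

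**The case against.** The best defence is that Section 10.2 is the operative design and is sound. Its hazards and ratio reproduce. A non-inferiority claim against an upper hazard ratio bound is directional, and 3 years of accrual with 2 of follow-up is stated. On that natural reading power is about 81% to 89%, so the claim of more than 80% is met. The error is then one outdated Summary sentence, and 25 patients remain justified. Much of this stands.

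Three stronger readings are tempting, and the documents do not support them.

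- A reader might infer that 85.6% was miscalculated. It was not shown to be; it is attainable for 95% vs 80%.
- A reader might infer that the 10.2 power claim is false or the trial underpowered. The lowest figure, about 50% to 54%, needs both a two-sided level and a 24-month cap, and 10.2 states neither.
- A reader might take 95% as the Summary's null and say the test would wrongly condemn a treatment with 90% control. If true control is 90%, a null of 95% is false and rejecting it is correct. Only a clash with the 10.2 target follows. As written, Section 10.3.1 would declare nothing, because it contains no test.

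The defence does not remove the contradiction between two current statements, supply the side and counted follow-up that 10.2 omits, or fill the gap in 10.3.1.

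**Conclusion.** The concern holds as an inconsistency. The Summary's rates and power do not describe the design that 10.2 justifies, and 10.3.1 does not settle which threshold applies. At the 10.2 expectation of 90%, with 80% as the null, the Summary's two-sided test has about 48% power (3+2 years, all follow-up counted) and 27-58% across the follow-up rules examined, not 85.6%.

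The 10.2 figure is conditional and not wrong. It holds one-sided with 3+2 years and all follow-up counted. It fails two-sided with the same follow-up (69-78% across methods) and one-sided with a 24-month cap (65-76%). Two-sided with 3+3 years it depends on the method (78% or 86%).

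These results rest on exponential failure, uniform accrual, no losses or competing deaths, 2-year rates in the Summary, and 80% as its null. The contradiction itself needs none of these assumptions.

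**What to change.** 1. In the Study Summary, replace the power sentence with the 10.2 hypotheses (unacceptable 2-year local control 75%, expected 90%) and remove 85.6%.
2. In the Summary and in 10.2, the sponsor should confirm that the test is a one-sample log-rank test, the side of the 0.10 level (the non-inferiority framing implies one-sided), and the follow-up per patient that counts: to 24 months, to 36 months, or all to data cut-off. Give one recomputed power with its method in both places. If it falls below 80%, restate the figure; whether that is acceptable for 25 patients is the sponsor's decision.
3. In 10.3.1, name the test or the matching confidence bound and the 75% threshold, and say how deaths are handled. An ordinary one-sample log-rank test censors deaths, whereas the planned estimate treats them as competing events, so inserting the test alone would create a new mismatch. Two consistent options are an upper confidence bound on 2-year cumulative incidence compared with 25%, or a log-rank test on the cause-specific hazard with deaths censored, reported beside the cumulative incidence.

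The cost is one Summary sentence, short edits to 10.2 and 10.3.1, and one power calculation. Treatment, eligibility and visits are untouched.

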1.0 BACKGROUND AND RATIONALE

1.1 Disease Background

Laryngeal cancer is the most common non-cutaneous head and neck malignancy affecting an estimated 13,430 patients in 2016 in the United States.[1] Over 75% of laryngeal cancers involve the true vocal cords or the glottic larynx, with over 90% of these cancers detected at early-stages (defined as carcinoma *in situ* and cT1-T2 tumors) when they are potentially curable using a single-modality. Local therapies are highly effective at curing early-stage glottic larynx cancer, as rates of nodal involvement and metastatic disease are less than 5%.[2-4] Treatment outcomes with radiation or surgical approaches for early-stage glottic cancer yield local control rates for Tis and T1 tumors typically greater than 90%, and for T2 tumors 70-80%, with ultimate local control rates exceeding 90% after surgical salvage.[2, 5]

Treatment Options

There are multiple voice-preserving local treatment options for early-stage glottic laryngeal cancer in the current NCCN guidelines.[6] These include conventional or minimally hypofractionated radiation therapy, transoral oral laser microsurgery (TLM) or open CO2 laser surgery, and hemilaryngectomy. Radiation therapy delivered in a small dose per fraction to the glottic larynx remains a common treatment for Stage Tis, T1, and T2 glottic tumors. Among 2338 patients treated with T1 glottic cancers in the Linked SEER-Medicare data files from 1991-2009, 47% were treated with radiation alone, 39% with local surgery and radiation, and 14% with local surgery alone.[7] Treatment with radiation therapy is typically delivered in 2 to 2.25 Gy daily fractions over 5.5-7 weeks.[8, 9] Endoscopic surgery via CO2 laser excision involves the removal of the gross tumor with a 2-3 mm margin thereby preserving the involved vocal cord while achieving reasonable voice outcomes.[10] Hemilaryngectomy is another surgical voice preservation option particularly for selected Stage T2 lesions where the involved vocal cord and paraglottic space are removed, with additional resection of the ipsilateral arytenoid and/or anterior commissure if involved.[10, 11]

Radiation Therapy Technique

Classically, early glottic larynx cancers were treated with an opposed lateral technique, were 2 opposing radiation beams were designed using a 5 x 5 cm or 6 x 6 cm field to cover the entire glottic larynx. This technique was effective and necessary before radiation treatments were able to be designed using CT planning, with the added ability of being able to measure dose to specific anatomic regions. With the advent of CT-based planning both 3D conformal radiation therapy (varying radiation fields to offer a more conformal dose distribution) and intensity modulated radiation therapy (IMRT; inverse radiation planning designed to limit the dose to specific organs while maximizing dose to a target), radiation treatment for early glottic larynx cancers has become more complex.

Carotid Sparing Radiation Therapy

Treatment using opposed lateral technique often includes both carotid arteries in the field, delivering a high dose to a ~5-6 cm of both carotid arteries. The data addressing the risk of stroke following radiation to the carotid arteries is controversial, although population-based studies have suggested an increase in late risk of ischemic events following radiation therapy of head and neck cancers.[12, 13] Because of the concern of unnecessary and potentially avoidable radiation therapy to the carotid arteries, dosimetric studies of early glottic larynx cancer began to emerge which demonstrating a significantly reduced radiation dose to the carotids with 3D conformal radiation planning and further dose reduction to the carotid arteries with IMRT.[14-17] Following these studies, many groups have begun to report outcomes with IMRT for treatment of early larynx cancers and all groups, thus far, have reported local control rates of >80%.[18-20]

Hypofractionated radiation therapy

Hypofractionated laryngeal irradiation initially began during World War II due to a shortage of hospital beds and despite the use of rather primitive radiation techniques, the cure rates were similar between 5 week and 3 week treatment courses.[21] In a more contemporary radiation setting, a randomized phase III clinical trial from Japan showed promising outcomes with a mildly hypofractionated radiation approach of 56.25-63 Gy in 2.25 Gy daily fractions for early stage glottic larynx cancer. The trial demonstrated an improved local control, of 92% vs. 77% at 5 years in favor of hypofractionation compared with conventional 60-66 Gy in 2 Gy daily fractions; the toxicity outcomes were similar with both approaches.[9] As a result of this trial, 63 (T1)-65.25 (T2) Gy in 28-29 fractions is one of the two recommended radiation regimens for early glottis cancer in the U.S.[22] These trials support the feasibility of moderate hypofractionation in the current clinical landscape. Extreme hypofractionation remains a possibility to improve both patient convenience and treatment cost.

In fact, we have completed a phase I dose-escalation trial of larynx stereotactic body radiotherapy (SBRT), and the results will be detailed throughout this discussion.

1.2 Study Agent(s)/Therapy(ies) Background and Associated Known Toxicities

Radiotherapy is well established and a recommended treatment for treatment of early glottic larynx cancer by the NCCN. Additionally, a few separate groups have reported outcomes with hypofractionated radiation regimens with minimal late grade 3 or greater toxicities.

Study	Site	Design	N	Stage	Fractionation	Dose / Fraction	Target	Late toxicities
Al-Mamgani et al, 2015[23]	Rotterdam, Netherlands	Prospective collected	30	T1a	58.08 in 16 fractions	3.63 Gy	Single cord	1/30 temp laryngeal edema
Ermis et al. 2015[24]	Yorkshire, UK	Retrospective		Tis- T2	55 Gy in 20 fractions	2.75 Gy	Larynx	1/132 (<1%) non-fx larynx
Laskar et al, 2012[25]	Mumbai, India	Retrospective	652	T1	50 Gy in 15 fractions, 55 Gy in 16 fractions, 60 Gy in 24 fractions, 62.5 Gy in 25 fractions	3.3 Gy, 3.43 Gy, 2.5 Gy, 2.5 Gy	Larynx	23.4% Persistent Laryngeal edema
Short et al, 2006[26]	Aukland, NZ	Retrospective	145	T1-T2	52.5-55 Gy in 20 fractions	2.63 Gy, 2.75 Gy	Larynx	One grade 3 toxicity
Gowda et al, 2003[27]	Manchester, UK	Retrospective	200	T1	50-52.5 Gy in 16 fractions	3.12 Gy, 3.28 Gy	Larynx	1/200 (0.5%) severe late toxicity

Table 1. Published hypofractionated radiation therapy studies addressing early stage larynx cancer with associated local control and late toxicities.

1.3 Other Agents

All patients on the study will be treated with radiotherapy alone.

1.4 Rationale

This study is premised on two related but different concepts. The first is that treatment volume reduction should lead to significantly improved acute and late laryngeal function, including voice and swallowing outcomes. The second is that for many patients, the treatment volume is small enough to compact the treatment schedule into just 5 fractions, which should lead to vastly

improved convenience. In fact, a shorter radiation therapy treatment course over 2.5-3 weeks, compared with the typical 5.5-6 weeks offers both a logistical advantage by improving not only the convenience, but also a potential cost advantage be requiring less treatment time on the machine.

A few considerations are necessary when considering treatment with highly focal radiotherapy, with or without extreme hypofractionation:

- Does focal treatment of the glottic larynx reduce dose to surrounding organs while offering similar rates of local control rates compared with treatment of the entire larynx?
- Can hypofractionated radiation therapy be delivered with acceptable acute and late toxicities?
- What treatment dose and fractionation is appropriate for the phase II portion of this trial?
- What radiation modality is the best option for delivery of dose-escalated, focal glottic larynx cancer?

Local control and organ sparing with a highly focal treatment

Based on data supporting focal IMRT technique for limiting radiation dose to the carotid arteries, a few academic groups have investigated a more focal radiation field by targeting the involved cord or site of disease, rather than unnecessarily radiating the entire larynx in every case. This highly-focused radiation therapy offers potential advantages, in both the ability to limit radiation dose to the uninvolved vocal cord, arytenoids, laryngeal cartilages, pharynx, spinal cord and carotid arteries, while allowing for dose-escalated radiation therapy to the disease itself.

A group from the Erasmus medical center recently published a report where they treated 31 patients with T1a glottic larynx cancers with single vocal cord irradiation to the entire cord using IMRT and daily cone beam CT scans for setup.[23] The clinical target volume (CTV) included the entire cord from a 1mm axial-sliced planning scan, as well as the maximal intensity projection from a 4D respiratory-gated CT scan. For tumors involving the anterior commissure (AC), the entire AC was included in the CTV. From the CTV, the group expanded 3mm circumferentially and 5mm superior-inferior for all but the initial 4 patients. With the reduced treatment volumes, they employed a higher dose per fraction at 3.63 Gy x 16 fractions and reported 100% local control at 2 years with no grade 3 or greater late toxicities. There was only 1 case of laryngeal edema in an actively smoking patient, and it fully resolved with steroids. Importantly, 78% of patients on this study were characterized as smoking. In addition, the median planning target volume (PTV) size was 10.6 cc, with a range of 8.1-13.7 cc. This is highly promising and supports the early results from our phase I trial, which will be described next.

For the phase I portion of our trial, we similarly focused our treatment volumes on the tumor alone and used a 4D CT gated breathing scan to develop the CTV with an added 2 mm, and then we circumferentially added a 3 mm PTV to create the final treated volume. A total of 30 patients were enrolled. With this highly focal treatment volume, we have achieved high local control rates of the first 2 dose levels (Figure 1) while substantially limiting the radiation dose delivered to nearby organs (Table 1). The 13 patients enrolled on the highest dose arm (42.5 Gy in 5 fractions) have not experienced any local failures thus far.

Figure 1. Kaplan Meier plots of local control of the first 2 dose levels including a) 4 patients treated with 50 Gy in 5 fractions with a 2-year actuarial local control of 75% (median follow-up 29 months [range 28-32]) and b) 12 patients treated with 45 Gy in 10 fractions with a 2-year actuarial local control of 84.4% (median follow-up 20 months [range 12-25]).

Safety of Dose-Escalated Radiation Therapy

Short et al, 2006[26]	52.5-55 Gy in 20 fractions	2.63 Gy, 2.75 Gy	66.3 Gy 70.1 Gy	98.5 Gy 105.4 Gy
Yamazaki et al, 2006[9]	63 Gy in 28 fractions	2.25 Gy	77.2 Gy	110.3 Gy

STU122017-043, [name], FormA-ResearchProtocol, Mod_29, 02-07-22

Conventional	66 Gy in 33 fractions 70 Gy in 35 fractions	2 Gy	79.2 Gy 84 Gy	110 Gy 116.7 Gy
--------------	--	------	------------------	--------------------

Table 3. Biologically effective doses (BED) of prior hypofractionated radiation regimens used for early stage glottic larynx cancer, assuming an α/β of 10 for a rapidly growing tumor, an α/β of 6 for a slow-moderate growing tumor and an α/β of 3 for late toxicities of normal tissues.

Given that patients with a larger PTV and active smoking history were at greater risk for toxicity (albeit encompassing only 3 patients in total) **in our study**, we have therefore decided to treat this population with the Dutch regimen. In particular, patients with:

- PTV greater than or equal to 10 cc
- Smoking within 1 month of registration

will be treated with daily SBRT at a dose of 58.08 Gy in 16 fractions. Because patients with small tumors from the phase I portion of the trial had minimal toxicity with treatment, we propose to continue the dose of 42.5 Gy in 5 fractions for tumors less than 10 cc.

Radiation Therapy Delivery

There are a number of different techniques used to deliver highly-focal, inverse planned radiation therapy. The Erasmus group used a static-field IMRT approach.[23] Static-field IMRT is a commonly used approach where the beam angles are pre-chosen and then the radiation delivery is inversely planned by the planning system. The downside of static-field IMRT is that 7-9 beam treatment requires up to 30 minutes to complete.

Another approach for treating a highly focal target that we employed in the phase I portion of the study, is to treat with a Cyberknife treatment planning system. The advantage of the Cyberknife system is that the radiation beams can be delivered from hundreds of different noncoplanar beam angles without manual adjustment of the treatment table. This technique proved to be effective given the high local control rates in the phase I portion of the trial, and it will be a treatment option for the phase II portion of the trial. However, the Cyberknife treatment planning system does have 2 specific drawbacks. First, unlike treatment planning systems that align patients prior to treatment using a cone-beam CT (CBCT) scan, the Cyberknife uses orthogonal x-rays to verify target position. Because the larynx isn't clearly visible using orthogonal x-rays, it must be tracked using fiducial markers. Fiducial markers placed either on the skin or subcutaneously outside of the larynx might not accurately represent where the larynx is located, especially if the patient has substantial external neck motion (i.e. substantial neck motion when breathing). The second limitation of using Cyberknife technology is the prolonged treatment time compared with other techniques. In the phase I portion of our study, the median treatment time on the Cyberknife was 38 minutes and ranged from 20-54 minutes. This is a long time to be positioned in an aquaplast treatment mask, provided there are suitable alternatives available, and it allows for more time where a mobile structure like the larynx can move out of the tracked treatment field (i.e. with swallowing).

A third option for treating a focal larynx cancer is with the use of volumetric modulated arc therapy (VMAT), which is essentially an IMRT treatment delivered from nearly 360 degrees around the patient. This allows for many more beam angles than static field IMRT and it also allows for a much quicker treatment. One group recently compared 2-arc VMAT with a typical 8-field IMRT plan for early stage larynx cancer and reported that both target volume coverage and homogeneity were comparable between VMAT and IMRT, while VMAT was superior for carotid-artery sparing. Additionally, VMAT delivery time was significantly faster than with IMRT (3-5 minutes vs. 5-10 minutes).[29] Another study supports the substantially reduced treatment time with arc therapy vs. IMRT.[30] Because of the promising results with VMAT treatment delivery, either modality (i.e. CyberKnife or VMAT) is acceptable for treatment on this protocol.

Summary points

- 1. Local control rates using a highly focal radiation target appear to be as good as conventional radiation therapy (≥80%)
- 2. Highly focal radiation therapy targeting only the involved site of disease plus a small margin delivers an extremely low dose of radiation dose nearby structures based on both the Dutch Erasmus and the UT Southwestern Phase I studies.
- 3. A reduced dose to nearby structures might improve toxicities, such as esophagitis and stroke from carotid atherosclerosis and could reduce the decline in voice function from contralateral cord dose. However, long-term follow-up of voice quality of life following focal larynx radiation therapy is not yet available from the phase I portion of this trial.
- 4. Hypofractionated radiation therapy appears to be safe, although there were three cases of soft tissue necrosis in the phase I trial. Current smoking status and larger PTV volume (> 10cc) all had qualitatively higher rates of necrosis.
- 5. Based on the phase I study, we propose using a dose of 42.5 Gy in 5 fractions for low-risk tumors: tumors with a PTV < 10cc, no recent smoking, and disease limited to the vocal process. This provides both an adequate tumoricidal dose, and a limited dose to normal tissues. Remaining patients will be irradiated using the Dutch 16 fraction regimen.
- 6. Treatment with either Cyberknife or VMAT will be acceptable.

With these observations, this study aims to maintain a high rate of local control while maintaining acceptable acute side-effects and improving late side-effects. We anticipate that this approach will improve late toxicities, patient convenience, and treatment cost. Moreover, because the delivered biologically equivalent dose is the same as conventional radiotherapy but delivered over a substantially shorter time period, it is also possible that local control will be superior with this technique as well.

